11.13. Appendix 13: How to identify the records for the interim analysis

This document defines the details how to apply the records to the interim analysis of BOTOX OAB 204947 from the released dataset(SIDATA), which includes the records won't be used for. Basically, described in the RAP, the records until 24weeks from the first treatment of each subject will be adopted for the analysis, however there are some data needed to be handled with particular handling rule. This document is provided to give a detailed description of these special handling rules as well as to suggest the physical structure of the analysis datasets from the aspect of data cutting.

Released data will be judged by record whether it should be included in the interim analysis or not, by comparing with the reference visit or date (Data cut visit or Data cut date) corresponding to 24 weeks of each subject. However, the Liver event and Cardiovascular event data will be decided for their adoption, by their specific rules described in chapter (2) and (3), instead of judgement by record.

(1) How to derive the reference visit or date (Data Cut Visit or Data Cut Date) corresponding to 24 weeks of each subject and the basic approach of judgement

Most of the records in SIDATA except for the records of Liver event or Cardiovascular event can be decided their adoption by comparing with the Data cut visit or Data cut date of each subject defined in below. Application of data cut type, i.e. visit or date, is determined by dataset considering its attribution. If the data is linked to particular visit in SIDATA, then it will be compared with Data cut visit by Visit number and will be adopted when it is smaller or equal to the reference. Data cut date will be used for the comparison with the relevant date of the logs data (i.e., AEs, conmeds, CIC etc.). The data up to or on Data cut date will be adopted.

The practical approach for each SIDATA will be described in chapter (4). Data cut visit(CUTVISIT), Data cut visit number (CUTVISN) and Data cut date(CUTDT) will be stored in ARDATA.MSTONE with Withdrawal until 24W (WDR24WFL), so that they can be used for the judgement in the process of ARDATA creation.

CONFIDENTIAL

204947

Condition 1	Condition 2	Data cut visit (Data cut visit number in 204947)	Data cut date
Withdrawn until 24W?	Last regular visit * ¹ of Treatment Cycle 1 In SIDATA.VISIT		
Subject without withdrawal until 24W DSCONT of 24w eq Y In DMDATA.DS	POST TX1 WEEK24 or later	POST TX1 WEEK24(170/300)	Visit date of the Data cut visit in SIDATA.VISIT, which will be imputed with “The date of first injection + 24 x 7” in the case of missing.
	POST TX1 WEEK18	treatment until 24w* ² : Twice	
		treatment until 24w: Once	
	POST TX1 WEEK12	treatment until 24w: Twice	
		treatment until 24w: Once	
	Others besides	POST TX1 WEEK24(170/300)	
Subject withdrew until 24W		Last visit of the subject in SIDATA.VISIT	Visit date of the Data cut visit in SIDATA.VISIT

*1 : Regular visits are the visits named with “TX1”, except the ones for the assessment of re-treatment or qualification, i.e. the visits named with “-add” in 204947.

*2 : Treatment until 24w doesn’t include the treatment just on 24w.

(2) How to make judgement of Liver Event data (with Visit number 8000s)

CONFIDENTIAL

204947

All of the liver event data (with Visit number 8000s) of the subject, to whom a liver event happens until 24W, will be adopted for the interim analysis. Whether the liver event happens until 24W or not will be judged by comparing the first detected date of liver event (LERSTDT in SIDATA.LEREPOR) and Data cut date of the subject, and if it starts before or equal to the reference date then the subject will be regarded with Liver event. This information will be stored in ARDATA.MSTONE as a variable of “Liver Event flag within w24 after 1st trt (LE24WFL)”.

(3) How to make judgement of Cardiovascular Event data (with Visit number 3000s)

None of the Cardiovascular Event data (with Visit number 3000s) will be used for the interim analysis. The patient profiles of CV events will be generated only at the end of the study, as defined in the display standard.

(4) The individual approach for the judgement of the adoption for the interim analysis

Following table shows the conditions to adopt the records for the interim analysis, which can be settled by dataset. The outcome of the judgement will be stored in a flag named as “Flag for interim analysis(ANLINTFL)” in each ARDATA. The records not used for the interim analysis will be included in ARDATA but will be excluded from the analysis by using “Flag for interim analysis”.

CONFIDENTIAL

204947

SIDATA	ARDATA	English Description	Visit num <3000 or logs data	Visit num 8000s (liver event data)	Visit num 3000s (Cardiovascular event data)	Note
demo	demo	Demography	all	-	-	No data cut required
exposure	exposure	Exposure	VISITNUM<=CUTVISN	-	-	
ds	ds	Subject disposition	Adopt all records, except for the subject logs data (VISITNUM eq 0) of the subject who continued after 24w MSTONE.WDR24WF L eq N).	-	-	Both of Visit data and logs data are involved
dv1	dv1	Protocol Deviations	DVSTDT <=CUTDT	-	-	
conmeds	conmeds	Concomitant medications	the records meet with any of following conditions will be adopted. 1) Compare the start date with the data cut date and adopt the	-	excluded	CV data can be identified with CONMEDS CMTYPCD eq 31

CONFIDENTIAL

204947

SIDATA	ARDATA	English Description	Visit num <3000	Visit num 8000s	Visit num 3000s	Note
		
smaller or equal to (CMSTDT<=CUTDT) . CMSTDT needs to be imputed as in RAP definition. 2) the records with 'CMPRIOR eq Y' will be adopted.
 
For OAB
 
3) the records of prior medicine for OAB (CMTYPCD eq 25) will be adopted.
 
For NDO
 
3) the records of prior medicine for NDO (CMTYPCD eq 224) will be adopted.
				
	cmanal	Concomitant medications analysis dataset	-	-	--	Carry flags from conmeds
blind	blind	Status of Treatment Blind	all	-	-	No data cut required
elig	elig	Eligibility (inclusion/exclusi	all	-	-	No data cut required

CONFIDENTIAL

204947

SIDATA	ARDATA	English Description	Visit num <3000	Visit num 8000s	Visit num 3000s	Note
		on)				
medhist	medhist	Medical History	all	If the subject's LE24WFL eq Y	excluded	
race	race	Collected race (check all that apply)	all	-	-	No data cut required
face	face	Findings About Clinical Event	VISITNUM<=CUTVI SN	-	-	
khqking2	khqking2	Kings Health Questionnaire King-2	VISITNUM<=CUTVI SN	-	-	
oabss	oabss	Overactive Bladder Symptom Score	VISITNUM<=CUTVI SN	-	-	Only for OAB
tbsm	tbsm	Treatment Benefit Scale - Modified	VISITNUM<=CUTVI SN	-	-	
ae	ae	Adverse Event	AESTDT <=CUTDT	-	-	
lab	lab	Laboratory Data	VISITNUM<=CUTVI SN <LE related records> If the subject's LE24WFL eq Y and		excluded	Liver Events visit numbers 8000s are not used in LAB in the current standard.

CONFIDENTIAL

204947

SIDATA	ARDATA	English Description	Visit num <3000	Visit num 8000s	Visit num 3000s	Note
		LAB.VISITDT is between LERSTDT and LERENDT of sidata.lereport				
ecg	ecg	ECG	VISITNUM<=CUTVISN	-	excluded	
vitals	vitals	Vital Signs Data	VISITNUM<=CUTVISN	-	excluded	
mo	mo	Morphology	VISITNUM<=CUTVISN	-		
surgery	surgery	Surgical procedures	SPDT<=CUTDT	-	excluded	
lereport	lereport	Liver event reporting	-	If the subject's LE24WFL eq Y	-	
subuse	subuse	Substance Use	all	If the subject's LE24WFL eq Y	-	
rucam	rucam	Liver Events RUCAM Scoring	-	If the subject's LE24WFL eq Y	-	
lbiopsy	lbiopsy	Liver Biopsy	-	If the subject's LE24WFL eq Y	-	
limaging	limaging	Liver Imaging	-	If the subject's LE24WFL eq Y	-	

CONFIDENTIAL

204947

SIDATA	ARDATA	English Description	Visit num <3000	Visit num 8000s	Visit num 3000s	Note
bacteria	bacteria	Bacteriology	VISITNUM<=CUTVISN	-	-	
ce	ce	Clinical Events	-	-	excluded	
cvdxtest	cvdxtest	Cardiovascular Events Diagnostic Tests	-	-	excluded	
dth	dth	Death event	DDDT<=CUTDT	-	-	
evidence	evidence	Physical Evidence	-	-	excluded	
facv	facv	Findings About Cardiovascular Events	-	-	excluded	
fadth	fadth	Findings About Death	all	-		
Famh	Famh	Findings about medical history	all			204948 only
Cc	CC		all			204948 only
EDSS	EDSS		all			204948 only

CONFIDENTIAL

204947

SIDATA	ARDATA	English Description	Visit num <3000	Visit num 8000s	Visit num 3000s	Note
famhist	famhist	Family History	all	-		
hru	hru	Healthcare Resource Utilisation	-	-	excluded	
nyhascr	nyhascr	NYHA Score	-	-	excluded	
risk	risk	Risks Factors	-	-	excluded	
ss	ss	Subject Status	VISITNUM<=CUTVI SN	-		

(5) Special Notes

- If the date of the record of logs data is missing then it will be excluded from the analysis.
- In the comparison of visit number. If the data of Unscheduled Visit exists in the same visit number of Data cut visit, it will be adopted as far as its visit number is smaller than the Data cut visit number precisely. i.e. if Data cut visit number = 1020, data with 1020.1 will be excluded from the analysis.

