11.4.1.2. Study Phases for AE Data and Safety Date except for AE

Treatment State	Definition
Pre-Treatment	AE Start Date $<$ 1st treatment Date
On-Treatment	If AE onset date is on or after treatment start date & on or before treatment stop date. 1st treatment Date \leq AE Start Date \leq Study Treatment Stop Date
Onset Time Since 1st Dose (Days)	If 1st treatment Date $>$ AE Onset Date = AE Onset Date - 1st treatment Date If 1st treatment Date \leq AE Onset Date = AE Onset Date - 1st treatment Date +1 Missing otherwise.
Duration (Days)	AE Resolution Date - AE Onset Date + 1
Treatment Cycle 1 (TC1) \leq 84 days from 1st treatment	1st treatment Date \leq AE Start Date \leq 1st treatment Date +83
Treatment Cycle 1 (TC1)	1st treatment Date \leq AE Start Date (if the subject completes / withdraws without 2nd treatment) \leq Study Exit/Withdraw Date

CONFIDENTIAL

204947

Treatment State	Definition
	or (if the subject take 2nd treatment) < 2nd treatment Date
GSK1358820 Treatment Cycle 1 (GTC1)	For subjects who received GSK1358820 as 1st treatment: 1st treatment Date ≤ AE Start Date (if the subject completes / withdraws without 2nd treatment) ≤ Study Exit/Withdraw Date or (if the subject take 2nd treatment) < 2nd treatment Date For subjects who received placebo as 1st treatment: 2nd treatment Date /Time ≤ AE Start Date / Time (if the subject completes / withdraws without 3rd treatment) ≤ Study Exit/Withdraw Date or (if the subject take 3rd treatment) < 3rd treatment Date
GSK1358820 Treatment Cycle 2 (GTC2)	For subjects who received GSK1358820 as 1st treatment: 2nd treatment Date /Time ≤ AE Start Date / Time (if the subject completes / withdraws without 3rd treatment) ≤ Study Exit/Withdraw Date or (if the subject take 3rd treatment) < 3rd treatment Date For subjects who received placebo as 1st treatment: 3rd treatment Date / Time ≤ AE Start Date / Time ≤ Study Exit/Withdraw Date
GSK1358820 Treatment Cycle 3 (GTC3)	For subjects who received GSK1358820 as 1st treatment: 3rd treatment Date / Time ≤ AE Start Date / Time ≤ Study Exit/Withdraw Date For subjects who received placebo as 1st treatment: Not applicable because 3 rd treatment of GSK1358820 is not allowed for subjects who received placebo as 1st treatment
Overall	For subjects who received GSK1358820 as 1st treatment 1st treatment Date ≤ AE Start Date ≤ Study Exit/Withdraw Date For subjects who received placebo as 1st treatment 2nd treatment Date ≤ AE Start Date ≤ Study Exit/Withdraw Date

NOTES:

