11.6.2. Study Population

Duration of Follow-Up instead of Extent of Exposure			

 Number of days of follow-up after study drug administration will be calculated based on the formula by Overall and TCs: 			
$\text{Duration of Follow-Up in Days} = \text{Date X} - (\text{Date Y}) + 1$			
For subjects who received GSK1358820 as first treatment			
Overall / TC for calculation	Subject status	X	Y
Overall	All subjects	Study Exit / Withdraw Date	1st treatment date
TC1	Study Exit or Withdraw in TC1	Study Exit / Withdraw Date [1]	1st treatment date
TC1	Receive next treatment	Date prior to 2nd treatment [1]	1st treatment date
GTC1	The same days as TC1		
GTC2	Study Exit or Withdraw in TC2	Study Exit / Withdraw Date	2nd treatment date
GTC2	Receive next treatment	Date prior to 3rd treatment	2nd treatment date
GTC3	All subjects in GTC3	Study Exit / Withdraw Date	3rd treatment date
For subjects who received Placebo as first treatment			
Overall / TC for	Subject status	X	Y

Duration of Follow-Up instead of Extent of Exposure					
calculation	All subjects	Study Exit / Withdraw Date	2nd treatment date (1st treatment date of GSK1358820)		
	Overall				
	TC1	Study Exit or Withdraw in TC1	Study Exit / Withdraw Date [1]		
	TC1	Receive next treatment	Date prior to 2nd treatment [1]		
	GTC1	Study Exit or Withdraw in GTC1	Study Exit / Withdraw Date		
	GTC1	Receive next treatment	Date prior to 3rd treatment		
	GTC2	All subjects in GTC2	Study Exit / Withdraw Date		
	GTC3	Not applicable, because GSK1358820 treatment is allowed only two times for subjects who received Placebo as first treatment in this study.			

 [1] In interim analysis, use the following date: 
 Date of withdraw date for subjects who do not receive 2nd treatment and withdraw before week 24 after 1st treatment Date of the Week 24 visit in treatment phase 1 for subjects who do not receive 2nd treatment and do not withdraw Date prior to 2nd treatment for subjects who receive 2nd treatment at the Week 12 / 18 visit in treatment phase 1 					
Duration of OAB history					

 Duration of OAB history is defined as the duration (years) from the date of diagnosis to the date of screening visit. 					

Identification of BPH

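### For subjects who leave by Week 24 without an exit visit on record, the interim cut date stops at their last recorded visit and drops dated events between that visit and withdrawal

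*SAP*

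**What the plan says.** Appendix 13 (SAP 11.13), added in the July 2018 amendment, defines which records enter the interim. For a subject who withdrew by Week 24, the cut visit is "Last visit of the subject in SIDATA.VISIT" and the cut date (CUTDT) is "Visit date of the Data cut visit in SIDATA.VISIT". Log-type records are then tested on their own dates: "The data up to or on Data cut date will be adopted".

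The dataset table in part (4) applies this as follows:

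- Adverse events: "AESTDT <=CUTDT".
- Surgery (which holds catheterisation, per Appendix 12), deaths and protocol deviations: the procedure, death or deviation date must be on or before CUTDT.
- Concomitant medications: the start date must be on or before CUTDT, apart from prior medication.
- Liver events, under part (2): the first-detected date is compared with the same CUTDT to set LE24WFL.
- Disposition (ds): "Adopt all records, except for the subject logs data" of subjects who continued past Week 24. Withdrawn subjects therefore keep everything. Findings About Death (fadth) is also kept in full.

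Elsewhere, SAP 3.1 says the interim datasets hold data up to 24 weeks after first treatment and are for regulatory submission. SAP 11.6.2, note [1], ends interim follow-up at "Date of withdraw date for subjects who do not receive 2nd treatment and withdraw before week 24 after 1st treatment". SAP 11.4.1.2 runs the first-cycle (TC1) adverse event window to the exit or withdrawal date.

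**The concern.** Appendix 13 stops at a visit; the other sections stop at withdrawal or at 24 weeks. The two agree when a withdrawal visit is held and recorded. They part when a subject dies, or leaves without coming back. The days between the last recorded visit and withdrawal are where an event that ended participation would often fall, so the lost records are not a random sample. Because disposition is kept, the interim can report a withdrawal for an adverse event or death with no matching adverse event record.

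The interim is the submission analysis. The 84-day safety tables (3.1 to 3.9 and 3.63 to 3.66) are marked for the interim only. They cover all adverse events, related events, fatal and other serious events, events leading to withdrawal, and events of special interest. Re-treatment needs at least 84 days since the previous injection (Protocol 5.3), so these tables compare the arms over one fixed window before any re-treatment.

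**Working it through.** The plan states no figure to reproduce, so the check applies the written rule to cases.

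**Inputs.** Visits fall at Weeks 0, 2, 6, 12, 18 and 24, which are Days 1, 15, 43, 85, 127 and 169 (Protocol 7.1; day count from SAP 11.6.1). Windows are ±3 days at Week 2 and ±7 days from Week 6. An adverse event is kept if its onset is on or before CUTDT, with CUTDT the last recorded visit. The 24-week limit is first treatment date + 24 × 7, which is Day 169.

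**Worked cases.** The comparison rule cuts at the withdrawal date, capped at Day 169.

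| Last recorded visit | Onset | Withdrawn | Appendix 13 | Withdrawal-date cut |
|---|---|---|---|---|
| Day 43 | Day 60 | Day 62 | dropped | kept |
| Day 1 | Day 9 | Day 10 | dropped | kept |
| Day 85 | Day 110 | Day 115 | dropped | kept |
| Day 43 | Day 40 | Day 62 | kept | kept |
| Day 62 (withdrawal visit) | Day 60 | Day 62 | kept | kept |

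The first three events are dated, lie within 24 weeks and occur before withdrawal, yet they are dropped. The last two rows show the limits: onset by the last visit, or a recorded withdrawal visit, keeps the event.

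**Length of the exposed gap**, if the subject leaves before the next scheduled visit:

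- After Week 0: 15 − 1 = 14 days; with windows 18 − 1 = 17.
- After Week 2: 43 − 15 = 28 days; with windows 50 − 12 = 38.
- After Week 6: 85 − 43 = 42 days; with windows 92 − 36 = 56. The gaps after Weeks 12 and 18 are the same.

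**What is never restored.** The 84-day tables cover Days 1 to 84. With a last visit on Day 43, the unrestored span is Days 44 to 84, or 41 days. With an early Week 6 visit on Day 36 it is Days 37 to 84, or 48 days. After a Week 12 visit on Day 85 it is nil. Losses after Day 84 affect only tables that are rerun at the final analysis.

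**Number of subjects.** The documents give no withdrawal rate. If 2% to 10% of 240 withdrew by Week 24, that is 4.8 to 24 subjects in both arms together. Those affected are a subset: no later visit recorded, and a dated event in the gap. One such subject is 1/120 = 0.8 percentage points of an arm.

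**The case against.** The strongest reply is that the protocol schedules a Withdrawal visit with adverse event collection, and the row in Appendix 13 refers to any visit in the dataset, not only regular ones. This stands: whoever has that visit recorded loses nothing with onset by that date. It does not help after a death or an unattended exit, and nothing in Appendix 13 says that such an exit creates a dated visit record.

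Several stronger readings are tempting, but the documents do not support them.

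- *Deaths vanish from the interim.* The fatal-event tables (3.63, 3.67, 3.87) are adverse event tables filtered on onset. A fatal event that began on or before the last visit stays in them. The death record (dth) is cut, but fadth is kept, and the one display devoted to deaths (Listing 47) is final-only.
- *Catheterisations are lost in number.* Protocol 7.4.7 ties the start of catheterisation to a residual volume measured at a visit, so it would normally start at a recorded visit.
- *Everyone lost to follow-up is exposed.* A subject the site cannot reach will seldom have dated events after last contact.
- *Rates are diluted because follow-up still counts the cut days.* The adverse event summaries are counts and percentages of subjects, so follow-up time does not enter them.
- *The loss is permanent throughout.* Cut records stay in the analysis datasets, and the TC1 and Overall tables are rerun at the final analysis. The tables by active-treatment cycle (GTC) are final-analysis displays.

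It is also fair to say that SAP 11.4.1.2 assigns events to phases and is not a data cut. The direct conflicts are with 3.1 and 11.6.2, and note [1] of 11.6.2 speaks only of subjects without a second treatment.

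**Conclusion.** The point holds for subjects who withdraw by Week 24 with no later visit recorded. For them the written rule removes adverse events with onset after the last visit and on or before withdrawal, including fatal serious events and events leading to withdrawal. It also removes death records, and any catheterisation, medication or deviation dated in the gap, and can leave the liver-event flag unset. This contradicts SAP 3.1 and 11.6.2 note [1] and is out of line with the TC1 window in 11.4.1.2.

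The gap is at most 42 days between scheduled visits, or 56 with windows, if no visit is missed before withdrawal. How many subjects are affected cannot be derived. The lasting loss is confined to the 84-day tables. The conclusion assumes that an unattended exit leaves no dated record in SIDATA.VISIT; if it does leave one, dated at withdrawal, the loss largely disappears.

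This should be fixed before the interim release. Few subjects are likely to be involved, but tables of fatal events and of withdrawals due to adverse events usually hold small counts, where one missing case can show.

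**What to change.** In Appendix 13 (1), for subjects who withdrew by Week 24, define the cut date for log data as

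CUTDT = later of [last visit date] and [earlier of (exit/withdrawal date, or death date if the subject died on study) and (first treatment date + 24 × 7)].

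The cap keeps the extension within the 24 weeks of SAP 3.1, and the outer term means no record now kept is lost. In the three dropped cases above, CUTDT becomes Day 62, Day 10 and Day 115, and all three events are kept. Apply it to ae, dth, surgery, conmeds, dv1 and the LE24WFL comparison. Leave the cut visit number (CUTVISN) as it is for visit-based data.

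Before release, check that every withdrawal for an adverse event or death in ds has a matching adverse event record flagged for the interim (ANLINTFL).

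The cost is one line of SAP wording, one line of derivation code and one reconciliation listing. No new data are needed.

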3. PLANNED ANALYSES

3.1. Interim Analyses

The interim planned primary analyses will be performed after the completion of the following sequential steps:

1. All subjects have completed treatment phase 1 (or week 24 of treatment phase 1, except for the premature withdraw) as defined in the protocol.
2. If the subject completes treatment phase 1 and receives 2nd treatment, this subject has completed the visit corresponding to 24 weeks after 1st treatment.
 - The subject who was re-treated at Week 12 visit in treatment phase 1 should complete the Week 12 visit in treatment phase 2.
 - The subject who was re-treated at Week 18 visit in treatment phase 1 should complete the Week 6 visit in treatment phase 2.
3. All required database cleaning activities have been completed and interim database release (DBR) and database freeze (DBF) has been declared by Data Management.
4. All criteria for unblinding the randomization codes have been met.
5. Randomization codes have been distributed according to RandAll NG procedures.

The interim analyses will be performed for regulatory submission. However subject level data will not be disclosed to people who work at the sites including investigators.

In interim analyses, the following analyses will be done with datasets which will include data until 24 weeks after 1st treatment.

- Study population
- Efficacy and safety analyses for treatment cycle (TC) 1(except for time to event analyses)
- Safety analyses for Overall period (i.e., the analyses for population “SP1”, which include subjects who had at least one GSK1358820 treatment)

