- If the study withdraw date is missing then the AE will be considered to be On-Treatment.
- AE start time needs to be considered if AE start date is equal to the re-treatment date
- As for safety date except for AE (i.e., laboratory data etc.), "AE Start Date" will be replaced with the date of measurement, unless otherwise specified.

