11.7.2.1. Handling of Missing and Partial Dates

Element	Reporting Detail
General	
 Partial dates will be displayed as captured in subject listing displays.
Adverse Events	
 The eCRF does not allow for the possibility of partial dates (i.e., only month and year) to be recorded for AE start and end dates. Completely missing start or end dates will remain missing, with no imputation applied. Consequently, time to onset and duration of such events will be missing. For example, this is the case for AEs status of 'ongoing' or AEs in interim analyses.
Concomitant Medications/ Medical History/OAB history	
 Partial dates for any concomitant medications recorded in the CRF will be imputed using the following convention: 
 If the partial date is a start date, a '01' will be used for the day and 'Jan' will be used for the month If the partial date is a stop date, a '28/29/30/31' will be used for the day (dependent on the month and year) and 'Dec' will be used for the month. The recorded partial date will be displayed in listings.

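### Undated adverse-event and catheterisation records are left out of the interim analysis for submission: incidence within an arm can only fall or stay the same, and the SAP's own missing-date section disagrees

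*SAP*

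**What the plan says.** SAP 3.1 states the purpose: "The interim analyses will be performed for regulatory submission". Appendix 13 (SAP 11.13), added by the July 2018 amendment, sets out how records are chosen. For data not tied to a visit, "Data cut date will be used for the comparison with the relevant date of the logs data (i.e., AEs, conmeds, CIC etc". The AE condition is "AESTDT <=CUTDT", which uses the AE start date. CIC is held in the surgery dataset (Appendix 12) and is selected in the same way on the procedure date. Special Note (5) then adds: "If the date of the record of logs data is missing then it will be excluded from the analysis".

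The exclusion applies to the interim only: "The records not used for the interim analysis will be included in ARDATA but will be excluded from the analysis by using" a flag.

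SAP 11.7.2.1 deals with missing AE dates separately. On entry it says: "The eCRF does not allow for the possibility of partial dates (i.e., only month and year) to be recorded for AE start and end dates". On handling it says: "Completely missing start or end dates will remain missing, with no imputation applied". The consequence it names is that time to onset and duration will be unavailable. It mentions AEs at the interim, and it does not say that the event leaves the incidence tables.

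**The concern.** An AE that happened but has no start date disappears from the incidence tables in the submission package, and no planned display counts such records. Other missing-date and missing-value rules in the SAP lean towards keeping the event. For a missing withdrawal date, SAP 11.4.1.2 says: "If the study withdraw date is missing then the AE will be considered to be On-Treatment". Missing causality is counted as related (SAP 11.6.4). Partial concomitant-medication start dates are completed before comparison with the cut date. A missing cut-visit date is imputed for subjects who continue to week 24. Undated AE and CIC records get no such protection.

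The loss is not always made good later. The AE tables for the first 84 days (3.1 to 3.9), and the matching fatal SAE, SAE, withdrawal and special-interest tables (3.63 to 3.66), are marked for the interim and not for the final analysis.

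**Working it through.** The plan gives no figure on this point, so there is none to reproduce. The check has two parts.

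**Direction and size.** Inputs:
- 120 subjects per arm (protocol 4.3).
- Background incidences on active and placebo from protocol 4.6.1: urinary tract infection (UTI) 26.4% and 10.1%; urinary retention 7.1% and 0.5%. These come from pooled overseas studies and serve only as illustration.
- The share m of affected subjects whose event is undated. The documents do not give it, so 0 to 10% is assumed, with one event record per affected subject.

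The safety populations in SAP section 4 are defined by treatment received, so the denominator stays fixed and

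observed incidence = p × (1 − m).

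| UTI, undated share | Active | Placebo | Difference (points) | Ratio |
|---|---|---|---|---|
| none | 26.4% | 10.1% | 16.3 | 2.61 |
| 2% in both arms | 25.9% | 9.9% | 16.0 | 2.61 |
| 5% in both arms | 25.1% | 9.6% | 15.5 | 2.61 |
| 10% in both arms | 23.8% | 9.1% | 14.7 | 2.61 |
| 10% in active only | 23.8% | 10.1% | 13.7 | 2.35 |
| 10% in placebo only | 26.4% | 9.1% | 17.3 | 2.90 |

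For example, with 10% in both arms: 26.4 × 0.90 = 23.76 and 10.1 × 0.90 = 9.09, a difference of 14.67.

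For retention with 10% undated in both arms: 7.1 × 0.90 = 6.39% and 0.5 × 0.90 = 0.45%, a difference of 5.9 points instead of 6.6.

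One subject lost from an arm is 1/120 = 0.83 points. For scale, the background placebo retention rate corresponds to 120 × 0.005 = 0.6 subjects.

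So (1 − m) never exceeds 1 and incidence within an arm cannot rise, while the difference and the ratio depend on how the undated records split between the arms.

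**The sections side by side.**
- SAP 11.7.2.1: the date stays missing, and time to onset and duration are lost.
- Appendix 13 (5): the whole record is lost from the interim.
- SAP 11.4.1.2: TC1, the first-84-day period, the GSK1358820 cycles and Overall are all defined by comparing the AE start date with treatment dates. An undated AE therefore belongs to no period. Deleting the Appendix 13 sentence would not by itself put the record into any table; a phase rule is also needed.

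**The case against.** The strongest reply is that undated records may hardly exist. Cleaning must be complete before the interim freeze (SAP 3.1). SAEs are reported within 24 hours (protocol 7.4.1.1), CIC start and completion dates must be recorded (protocol 7.4.7), and a UTI adverse event rests on a culture result, usually from a dated visit (protocol 7.4.6.2.2). The examples in SAP 11.7.2.1, ongoing events and events at the interim, most naturally mean missing end dates, and the interim rule uses the start date. The ban on partial dates could push a site to leave a month-only event undated, but the documents do not say what sites do. The proportional calculation is also an upper bound, because a subject with a second, dated event of the same kind still counts. All of this stands and limits the size of the problem. It does not remove the conflict between the two sections.

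Excluded records stay in the datasets, and the TC1 and Overall AE tables are rerun at the final analysis. That stands too, except for the interim-only 84-day tables.

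Two stronger readings are tempting and are not supported:
- A reader might infer that the rule can only understate the drug's harm. It cannot be put that strongly: if undated records fall mainly in placebo, the excess on active is overstated, and an undated event that truly began before treatment or after the cut is rightly left out.
- A reader might infer that a death with no recorded date would vanish altogether. Appendix 13 does select the death dataset by death date, but death is not named among the log data and the findings about death are kept in full. The death listing (47) is a final output. The interim fatal-event tables (3.63, 3.67, 3.87) are AE displays and on the ordinary reading follow the AE start date, so a fatal event with a dated onset would still appear.

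**Conclusion.** The point holds, with limits. AE and CIC records with a missing date are excluded from the interim analysis done for submission. Within each arm this can only lower the reported incidence or leave it unchanged, and the between-arm contrast has no fixed direction. The rule conflicts with SAP 11.7.2.1, and for the first-84-day tables the interim is the only chance to count the event.

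The size is unknown, because the documents give no number of undated records and it may be zero. On the assumed shares of 2% to 10%, a UTI incidence of 26.4% would read 25.9% to 23.8%. Each lost subject costs 0.83 points, which matters mainly for rare events. The conclusion about direction rests only on denominators being independent of event dates; the size rests on the assumed share and on one event record per affected subject.

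**What to change.** Replace the sentence in Appendix 13 (5), for AE and CIC (surgery) records, with a rule on these lines:
- Keep an undated record in the interim incidence tables unless its end date or other data place it before first treatment, or other data place its onset after the cut date.
- Assign it to TC1 and, on the same basis, to the first-84-day tables. For subjects given GSK1358820 first, count it in Overall as well.
- For placebo subjects re-treated before the cut, also count it in the active-exposure Overall tables unless other data place it before re-treatment. A plain TC1 default would put a possible active-drug event into placebo time and out of Overall, which for these subjects starts at the second treatment.
- List the undated records and count them by arm.

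Bring SAP 11.4.1.2, 11.7.2.1 and Appendix 13 (5) into line with this rule. For deaths, only state how a missing death date is handled in the death dataset.

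The cost is a few sentences and a few lines of programming. Incidences may come out slightly higher, and an undated event in a re-treated placebo subject can appear in both the placebo TC1 table and the active Overall table, which a footnote should say. If no record is undated, nothing changes.
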